4.2 Recruitment Plan

After IRB approval, subjects with upper extremity spinal cord injuries will be recruited through: 1) an internal search, match, and communication of subject records within Courage Kenny Rehabilitation Institution performed by an out-patient care coordinator and/or PI, 2) this trial will be posted and listed on www.clinicaltrials.gov with contact information available for possible enrollment of this study. Due to the size (n=3-6) of this study and recruitment methods, issues with recruitment of subjects is not anticipated. A list will be compiled and pre-screened by the principal investigator.

Potential study participants will be contacted by a research clinician to determine their interest in participating in the APEX pilot study. Consent forms will be sent out in advance of focus group session. The consent form will be reviewed with the potential study participants in a group setting.

5. Evaluations

5.1 Pre-study Evaluations

As part of the Screening, potential subject medical records will be evaluated by a clinician at Courage Kenny Rehabilitation Institute to match inclusion or exclusion criteria. No data will be collected or recorded until an informed consent form is reviewed and signed by the study participant. Patients who have indicated that they are not willing to provide access to their medical records for screening purposes (MRA 'No') will not be screened for study participation.

5.2 Evaluation During Study

During the visits, subjects will be assessed and supervised by the PI and/or the co-collaborators. Subjective and Objective tests and data will be collected for data analysis.

5.3 Post-Study Evaluations

None of the subjects will be followed or have data recorded after the visit, unless an adverse event is reported that relates to their participation in this study.

6. Outcomes

The fundamental purpose of conducting this pilot study is to examine the feasibility and safety of an APEX device, and examine the feasibility of an approach to ultimately be used in a larger scale study. Upon successful completion of the APEX Pilot Study, AbiliTech plans to submit for a Phase II NIH grant to complete product and clinical development on the path to commercial release of the APEX device.

The APEX Pilot Study includes assessments and other metrics that measure function and gather feedback as listed in Table 3.

Concept model device feasibility will be subjectively evaluated and defined as follows:

1. Manipulation of Mannequin: Were the users able to control the device with intention?
2. Usability Outcomes: User feedback on device performance, user input controls and overall comfort.
3. Clinician Feedback: Are there features that should be integrated into the device to enhance clinical utility?

Principal Investigator and Clinician feedback on overall device performance will be factored into the concept model feasibility results.

7. Criteria for Study Discontinuation

AbiliTech Medical will document any study participant subject discontinued from the APEX pilot study. The documentation will contain the rationale for study participant subject to be discontinued from the study. The PI must be notified immediately if a study participant subject discontinues the pilot study. Any data from the discontinued study participant subject will be maintained and may be used in the data analysis.

A study participant subject in this study may be discontinued for any of the following reasons:

- At the Investigator's discretion;
- At the subject's discretion;
- If the subject has a severe injury or illness within or outside of the study that affects their participation in the study;

8. Statistical Considerations

Data will be recorded and reported. No statistical analysis will be performed since the subject population is n=3-6. This study is designed to assess early feasibility and prepare for a larger clinical study in the future.

9. Retention of Records

In compliance with the ICH/GCP guidelines the investigator will maintain all CRFs and all source documents that support the data collected from each subject, and all trial documents as specified in Essential Documents for the Conduct of a Clinical Trial and as specified by the applicable regulatory requirement(s). The investigator will take measures to prevent accidental or premature destruction of these documents. Essential documents will be retained until at least two years after the last approval of a marketing application in an ICH region or at least two years have elapsed since the formal discontinuation of clinical development of the investigational product. These documents will be retained for a longer period if required by the applicable regulatory requirements or by an agreement with the sponsor. These documents will be retained for a longer period if required by Abbott Northwestern Hospital policies and procedures.

Original documents will be secured in a locked cabinet in the Courage Kenny Research Center. Copies that do not identify the study participant human subjects (using a code such as AMI-CKRI-XXX) may be shared with AbiliTech Medical for data and evaluation. AbiliTech will store the data in a locked cabinet on company premises with restricted access. Electronic copies with de-personalized data may be analyzed in an excel file. De-identified survey results will be collected and stored in Survey monkey web application for data analysis. Audio recordings will be transcribed and de-identified. Video recordings will be of device function and not of focus group participants.

10. Amendments to the Protocol

All protocol amendments will be submitted to the IRB. Amended protocol will be reviewed, approved and documented by the same method as the original protocol was reviewed and approved. Once the amended protocol and all associated documents are reviewed and approved, the most recent protocol version and effective date will be changed on all pages of the protocol. Study personnel will be notified of any protocol deviations.

11. Deviations from Investigative Plan

The Investigator is not allowed to deviate from the clinical investigation plan. Under emergency circumstances, deviations from the protocol to protect the rights, safety and well-being of human subjects may proceed without prior IRB. Such deviations shall be documented and reported to the IRB as soon as possible.

Deviations will be reported in a site-specific deviation/violation log. Serious protocol violations will be reported in writing, with the corresponding log to the IRB within 24 hours.

12. Informed Consent Process

Potential study participants will be contacted by a research clinician to determine their interest in participating in the APEX pilot study. Consent forms will be sent out in advance of focus group session. The consent form will be reviewed with the potential study participants in a group setting.

The investigator and Research Staff will be responsible to assure that informed consent has been provided by a subject before study participation.

Prior to carrying out any protocol-specific procedures, investigators or designated staff will fully explain the details of the protocol, study procedures, and the aspects of subject privacy concerning research specific information. The original signed documents will become part of the subject's medical record, and each subject will receive a copy of the signed documents. All subjects must provide written informed consent prior to registration and treatment.

The following points will be observed during the informed consent process:

- a) The principal investigator or her authorized designee conducts the informed consent process
- b) All aspects of the clinical investigation that are relevant to the subject's decision to participate will be included
- c) Any coercion or undue improper influence on, or inducement of, the subject to participate will be avoided
- d) Ample time for the subject to read and understand the informed consent form and to consider participation in the clinical investigation will be used
- e) Personally dated signatures of the subject and the principal investigator or an authorized designee responsible for conducting the informed consent process will be included in the informed consent form
- f) The subject will be provided with a copy of the signed and dated informed consent form and any other written information
- g) Important new information will be provided to new and existing subjects throughout the clinical investigation

Subjects that are unable to provide consent on their own will not be included in this study.

13. Reporting Requirements

The reporting plan for this study to relevant regulatory agencies will be as follows:

Progress Reports or Annual Reports

- Will be submitted at least once a year to reviewing IRB.

Study Completion or Termination

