Target user population will be three to six individuals with spinal cord injury at levels C3 to C5, and AIS A, B, or C. Inclusion and exclusion criteria are below:

3.1 Inclusion Criteria:

1. Spinal cord injury at levels C3 to C5, and AIS A, B, or C
2. Greater than 3-months post injury or surgery to spinal column, arms, or shoulder
3. Ability to provide informed consent
4. Age 18 or over
5. Selected for participation based on investigator discretion

3.2 Exclusion Criteria:

1. Unable to follow instructions
2. Exhibit significant behavioral problems or impaired cognitive ability
3. Inability to provide consent
4. Non-English speaker

Clinicians involved in overseeing the device manipulation portion of the study will be expected to provide feedback about the APEX device.

4. Study Design

Part 1: The study design will be that of a single-arm pilot study with three to six human subjects (n=3-6). The study will inform the AMI design team of customer and APEX design requirements needed to develop an APEX device for commercial release. Participants will be expected to attend one 180 minute session. AbiliTech Medical personnel will be present for user training, during all device evaluation sessions and to troubleshoot technical problems. Courage Kenny Rehabilitation Institute (CKRI) personnel will collect subject medical history from medical records once consent and HIPAA authorization are obtained. Appendix 1, section 1 includes subject information to be collected. Potential participants will receive the consent form ahead of time to read and study. At the start of visit 1, subjects will be consented as a group and sign the HIPPA authorization. During device testing, Appendix 2 and 3 include assessment forms for device testing and questions subjects will be asked. Appendix 4, includes the device feedback survey which will be completed onsite before conclusion of the study. Subjects will use their personal internet connected mobile device to access and complete the survey. If subjects do not have a mobile device, a tablet will be available for subject to use and complete the survey. Audio recordings will be taken and videos of the mannequin will be recorded during device movement. Table 1 highlights activities to be performed in the User Focus Group.

Table 1: Visit 1: User Focus Group Activities

	Activity	Description

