1: Consent (Up to 30 minutes)	1.1: Review and Sign Informed Consent Form (0-30 minutes)	Study participants will review and sign consent form in a group setting. They will be given time as to review and provide consent. Consent forms will be mailed to scheduled participants in advance of the focus group session.
2: Device Testing and Follow up (approximately 90 minutes)	2.1: Device Instructions and Operational Testing (60 minutes)	The clinician and AbiliTech Personnel will describe to the user on how to operate the device. The study participant will acclimate to use of the device. Data will be collected on the operation, function, and performance of the APEX device. Safety risks will be assessed.

	2.2: Device & Follow Up (10-15 minutes)	The study participant will provide feedback about their experience with the device.
3: Device Feedback (approximately 30-60 minutes)	3.1 Complete Survey	Subject performs Survey Monkey Survey on Device Preferences. Compensation provided upon survey completion.

Part 2 of the study will comprise of a clinician focus group to evaluate data gathered in the user focus group, AbiliTech bench testing, and motion capture data of the device function. Appendix 5 includes questions for clinicians to answer. Table 2 highlights the Clinician focus group activities.

Table 2: Visit 2: Clinician Focus Group Activities

	Activity	Description
1: Data Review (approximately 60 minutes)	1.1: Study Data Presentation	AbiliTech Medical will present data to CKRI clinical team. Data includes User focus group results and results device bench testing.
2: Device Feedback (approximately 60 minutes)	2.1 Discussion on Device	Clinicians and AbiliTech Medical team members will discuss the safety and clinical utility of the APEX device.

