Appendix 2: Pilot Usability Testing Form

[name]
[contact] www.abilitechmedical.com

AbiliTech Medical APEX Study Pilot Usability Testing Form

Subject Information

Subject ID Number _____

Subject Assessment with APEX

Is the subject familiar with smartphone applications? Yes No

Can the subject use voice control features of the application to toggle between device modes? Yes No

Can the subject use the head worn accelerometer to control the APEX device movement? Yes No

Can subject power the device on/off? Yes No

Can the subject move the APEX on a mannequin in the following Ranges of Motion?

Shoulder

Flexion Powered ROM: 0 to 60° Yes No

Shoulder Abduction Powered ROM: 0 to 30° Yes No

Horizontal Internal Rotation Powered ROM: 35 to -35° Yes No

Compound Shoulder ROM (Flexion, internal rotation, horizontal adduction: limited in horizontal plane): 0 to 100° Yes No

Elbow

Elbow Flexion/Extension Powered ROM: 0 to 130° Yes No

Forearm

Supination Powered ROM: 0 to 60° Yes No

Pronation Powered ROM: 0 to 50° Yes No

Can the subject move the APEX on a mannequin to complete the following tasks?

Control APEX device to manipulate objects in space Yes No

Control APEX to move an object in a preferred pathway Yes No

Control APEX device to push buttons Yes No

Control APEX to lift a water bottle from table level Yes No

Control APEX to lift a phone Yes No

Uncontrolled device movement observed: Yes No (if yes, please comment below)

Time spent using the device: _____ (min)

Notes

Utility

1. On a scale of 1 to 5, how would the APEX System improve your ability to use your arms? (1 no improvement - 5 strong improvement)
2. In general, what would you like to be able to do with your arms?
3. What are three to five Activities of daily living that you wish you could perform, listed in priority?
4. Do you think using the APEX device you could do [each of the ADL they stated]?

Device Feedback

1. What is your general impression of the APEX System, knowing the development phase it is in?
2. Would you use the APEX System? How much? Where? When? For what Uses?
3. What do you like about the APEX System?
4. What do you dislike about the APEX device?

5. What could be improved about the APEX device?
6. What is your opinion about the size, appearance, texture, color, and/or noise of the APEX device?
7. What is your opinion on the control system?
8. What type of control system would you prefer?

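### Does the optional use of a discontinued subject's data let a failed task or an uncontrolled movement drop out of the report?

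*Combined protocol and SAP*

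**What the plan says.** Section 7 (Criteria for Study Discontinuation) sets the rule for early stoppers: "Any data from the discontinued study participant subject will be maintained and may be used in the data analysis". One listed ground for stopping is "At the Investigator's discretion". The sponsor must document each discontinuation with its rationale, and the PI must be told at once.

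Section 8 (Statistical Considerations) states "Data will be recorded and reported" and rules out statistical analysis because of the sample size of 3 to 6. The synopsis, under Evaluation of Outcomes, likewise says the data are reported without statistical analysis and the functional and safety outcomes are compiled and reviewed. Neither place defines an analysis set or a denominator, and neither exempts discontinued subjects.

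Section 6 (Outcomes) makes feasibility a subjective judgement and adds: "Principal Investigator and Clinician feedback on overall device performance will be factored into the concept model feasibility results". Appendix 2 records each task as Yes or No. Its safety line reads "Uncontrolled device movement observed: Yes No (if yes, please comment below", and the form also has a time-on-device entry and a Notes field.

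**The concern.** Read alone, Section 7 lets someone choose whether a discontinued subject counts, and that choice can be made with the result known. Section 5.2 says "subjects will be assessed and supervised by the PI and/or the co-collaborators". Section 4 says "AbiliTech Medical personnel will be present for user training, during all device evaluation sessions and to troubleshoot technical problems". Nothing is blinded, and no one is named as deciding on inclusion, by any rule or at any set time.

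The summary also has consequences. Table 2 says "AbiliTech Medical will present data to CKRI clinical team" at Visit 2, and clinician feedback then feeds the feasibility conclusion. With so few subjects and no interval or model, the counts are the whole quantitative result, so one missing subject could turn a mixed picture into a clean one. Because the task lines offer only Yes or No, an early stopper who never reached a task also has no obvious code.

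**Working it through.** **Inputs.** n = 3 to 6, single arm (Section 4). Tasks and uncontrolled movement are Yes/No (Table 3). The documents give no discontinuation rate, no success threshold and no power or interval calculation, so there is no figure in the plan to reproduce.

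**Step 1: what an omission would do.** Suppose one subject fails a task, the rest succeed, and the failing subject is discontinued and left out. The count moves from (n−1)/n to (n−1)/(n−1), a shift of 1/n. If instead that subject had the only uncontrolled movement, 1/n becomes 0/(n−1).

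| n | Task, all counted | Task, one omitted | Shift (points) | Movement, all counted | Movement, one omitted |
|---|---|---|---|---|---|
| 3 | 2/3 = 66.7% | 2/2 = 100% | 33.3 | 1/3 = 33.3% | 0/2 |
| 4 | 3/4 = 75.0% | 3/3 = 100% | 25.0 | 1/4 = 25.0% | 0/3 |
| 5 | 4/5 = 80.0% | 4/4 = 100% | 20.0 | 1/5 = 20.0% | 0/4 |
| 6 | 5/6 = 83.3% | 5/5 = 100% | 16.7 | 1/6 = 16.7% | 0/5 |

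The arithmetic is right, but it holds for any study of this size once one adverse result is deleted. It says nothing about whether deletion will occur.

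**Step 2: how often the rule could come into play.** With an assumed discontinuation probability d per subject, P(at least one) = 1 − (1−d)^n.

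| d (assumed) | n = 3 | n = 6 |
|---|---|---|
| 5% | 14.3% | 26.5% |
| 10% | 27.1% | 46.9% |
| 20% | 48.8% | 73.8% |

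These are upper bounds on the chance of a harmful omission, because the discontinued subject must also have an adverse result and then be left out. The bound is not negligible at the higher assumed rates, so the conclusion should not rest on rarity alone.

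**Step 3: which rule governs reporting.** Section 7's permissive verb concerns use in an analysis. Section 8 says there is no statistical analysis and that data are reported. Read together, they leave Section 7 most naturally as permission to go on using data after a subject leaves. The reporting duty in Section 8 and the synopsis is untouched. Failing a task is not a listed ground for discontinuation, and a subject who fails and finishes the session is outside Section 7 altogether.

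**Step 4: whether an omission would go unseen.**
- Clinicians who oversee device manipulation are the ones expected to give feedback (Section 3).
- Clinic staff monitor subjects for the whole time they control the device (Section 14).
- The mannequin is filmed during device movement (Section 4).
- Original documents stay at the clinic, and the sponsor may receive coded copies (Section 9).
- Conclusions come from the sponsor and the Allina investigators together (synopsis, Evaluation of Outcomes).

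At least part of the clinical side would therefore have seen a failed task or uncontrolled movement directly.

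**Step 5: the form.** A task that was not reached can be left blank and explained under Notes, and time on device shows how far the subject got. A separate box would be tidier, but the information already has a place.

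**The case for a change.** The best argument for a change is that the specific rule should prevail over the general one. Section 7 addresses discontinued subjects by name and says their data may be used; Section 8 does not mention them. Reading Section 7 as permission after withdrawal still leaves use optional. Documented rationales and retained records make an omission traceable but do not require the data to appear in the report or in the Visit 2 presentation. Where descriptive counts are the only result, a complete denominator is the main safeguard, and a sentence or two would secure it.

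Part of this stands. No section expressly requires that a discontinued subject be counted, and the two sections could be better aligned. What does not follow is that the plan as written leads to a biased result. Section 8 can be followed in full without breaching Section 7, and doing so gives a complete report. Bias needs the discretion to be misused, and nothing in the documents suggests that is planned. A compulsory rule would also bind subjects who leave by their own choice, and the consent terms on withdrawn data are not among the documents reviewed.

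**Conclusion.** No change is needed. This is missing detail that a competent analyst fills sensibly: report every subject who started testing, give the number discontinued with reasons, and note tasks not reached. The possible distortion is 1/n, or 17 to 33 points on a task count, and the loss of a lone uncontrolled movement from the summary. It arises only if an adverse result, a discontinuation and a choice to omit all coincide. No test, interval or decision threshold depends on the count.

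This conclusion assumes that the reporting statements in Section 8 and the synopsis cover everyone tested, as their unqualified wording suggests, and that the clinic's oversight and record-keeping work as described. It does not rely on any particular discontinuation rate, since none is given.

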Appendix 1: Medical History Report Form

[name]
[contact] www.abilitechmedical.com

AbiliTech Medical APEX Study Medical History Report Form

Subject Information

Subject ID Number _____ Year of birth _____ Height (in) _____ Weight (lbs) _____

Diagnosis: _____ Level of Injury: _____ AIS Score: _____

MMT Scores: Shoulder Flexion _____ Adduction _____ Elbow Flexion _____ Elbow extension _____

Forearm Pronation _____ Forearm Supination _____

Hand dominance: Left Right **Gender:** Male Female

Subject Meets Inclusion/Exclusion Criteria: Yes No **Year of Injury:** _____

Subject Participating in another clinical trial: Yes No _____ (if yes, please list trial)

Wheelchair mfr/model _____ / _____ **Independent mobility/balance (please check category that best describes subject ability)** Ambulatory Supine to sit Sit to stand

Notes

Appendix 2: Pilot Usability Testing Form

[name]
[contact] www.abilitechmedical.com

AbiliTech Medical APEX Study Pilot Usability Testing Form

Subject Information

Subject ID Number _____

Subject Assessment with APEX

Is the subject familiar with smartphone applications? Yes No

Can the subject use voice control features of the application to toggle between device modes? Yes No

Can the subject use the head worn accelerometer to control the APEX device movement? Yes No

Can subject power the device on/off? Yes No

Can the subject move the APEX on a mannequin in the following Ranges of Motion?

Shoulder

Flexion Powered ROM: 0 to 60° Yes No

Shoulder Abduction Powered ROM: 0 to 30° Yes No

Horizontal Internal Rotation Powered ROM: 35 to -35° Yes No

Compound Shoulder ROM (Flexion, internal rotation, horizontal adduction: limited in horizontal plane): 0 to 100° Yes No

Elbow

Elbow Flexion/Extension Powered ROM: 0 to 130° Yes No

Forearm

Supination Powered ROM: 0 to 60° Yes No

Pronation Powered ROM: 0 to 50° Yes No

Can the subject move the APEX on a mannequin to complete the following tasks?

Control APEX device to manipulate objects in space Yes No

Control APEX to move an object in a preferred pathway Yes No

Control APEX device to push buttons Yes No

Control APEX to lift a water bottle from table level Yes No

Control APEX to lift a phone Yes No

Uncontrolled device movement observed: Yes No (if yes, please comment below)

Time spent using the device: _____ (min)

Notes

Utility

1. On a scale of 1 to 5, how would the APEX System improve your ability to use your arms? (1 no improvement - 5 strong improvement)
2. In general, what would you like to be able to do with your arms?
3. What are three to five Activities of daily living that you wish you could perform, listed in priority?
4. Do you think using the APEX device you could do [each of the ADL they stated]?

Device Feedback

1. What is your general impression of the APEX System, knowing the development phase it is in?
2. Would you use the APEX System? How much? Where? When? For what Uses?
3. What do you like about the APEX System?
4. What do you dislike about the APEX device?

5. What could be improved about the APEX device?
6. What is your opinion about the size, appearance, texture, color, and/or noise of the APEX device?
7. What is your opinion on the control system?
8. What type of control system would you prefer?
9. What is your opinion on the user interface?
10. What improvements in the control system or user interface would you like?
11. Would you be interested in predefined pathways of motion to assist in control of the device?
12. What safety concerns do you have about the APEX system?
13. What could be done to minimize these risks?

